#### Other Items as applicable:

- **Appendix A - Children**
- **Appendix B - Drug/Device**
- **Appendix C- Multi Site Research**
- **Appendix D- Pregnant Women and Neonates**
- **Appendix E- Prisoners**
- **Appendix F- Waiver of Consent/ PHI**
- **Appendix G- Exception from Informed Consent (EFIC)**
- **Appendix H- Native American**
- **Biosafety Review letter** (for UA - Institutional Biosafety Committee)
- **Certificate of Confidentiality**
- **Compressed Gases Review letter** (for UA – Research Instrumentation)
- **Contract** – complete or draft copy of contract including budget
- **Data Collection Tools** – surveys, questionnaires, diaries not included in the protocol, data abstraction form for records review
- **Data Monitoring Charter and Plan**
- **Drug/Device information** – Investigator's Brochure, drug product sheet, device manual, user's manual, instructions for use, package insert, IND/IDE documentation, FDA 1572 form, 510k indication, FDA exemption, sponsor determination of device risk, etc.
- **Export Control Review**

- **Grant Application(s)** – cover-to-cover copy of grant, regardless of home institution or funding agency, and a copy of the Notice of Grant Award.
- **Multi-site information** (for sites engaged in research where the UA is the IRB of record)
  - Copy of any approvals granted from that site (including determinations if this site has an IRB of its own)
  - Site-specific F107
  - Copy of the site's human subjects training policy
  - CV and medical license (if applicable) of site PI
- **Other Approval letters** (e.g., school districts, Tribal, other IRB approvals)
- **Participant Materials** – written materials to be provided to or meant to be seen or heard by subjects (e.g. study newsletter, physician to participant letter, wallet cards, incentive items, holiday/birthday cards, certificates, instructional videos/written guides, calendars, certification of achievement, etc.)
- **Payer coverage analysis**
- **PHI Authorization Form(s)**
- **Protocol** – including all amendments/revisions, sub- or extension-studies
- **Radiation Safety Review** letter- needed regardless if the radiation device is approved and used standard of care
- **Recruitment Materials** – telephone scripts, flyers, brochures, websites, email texts, radio/television spots, newspaper advertisements, press releases, etc.
- **Scientific Review Committee** letter (for cancer related projects – AZCC SRC; other units as applicable if the unit has a scientific review committee)
- **Site Authorizations** for research purposes and/or access to administrative records/samples
  - External sites (such as schools, other hospitals or campuses, etc.)
  - UAHS Research Portal feasibility review approval
- **Travel Authorization documentation** (for UA – Office of Global Initiatives)
- **Use of retrospective research samples and/or data** – IRB approval letter, original consent under which samples/data were collected, letter allowing access to samples

Work Should Not Hurt You: Reduction of Hazardous Exposures in Small Businesses
Through a Community Health Worker Intervention

ClinicalTrials.gov ID NCT03455530

PI: [name] (University of Arizona)

Statisticians: [name] supervised by [name] (University of Arizona)

January 16, 2024

Statistical Analysis Plan

Descriptive statistics will be calculated for shop and participant characteristics. Differences in baseline characteristics between the immediate and delayed intervention groups will be tested using the Welch Two-Sample t-test for continuous variables and Fisher's Exact Test for categorical variables. For all analyses, all tests will be two-sided, with a p-value < 0.05 considered statistically significant.

To analyze the primary outcome TVOC data, we will use linear mixed models to account for the lack of independence from repeated measurements within a shop at an assessment and across assessments. We will use contrasts to test the change in TVOC concentration from pre- to post-intervention between the arms. To account for possible confounding, we will fit both unadjusted and adjusted models. The unadjusted model has log-transformed TVOC concentration as the outcome, with fixed effects for intervention group (immediate, delayed), assessment time (1, 2, 3), and their two-way interactions; random effects will be included for shop and assessment time within shop, with random intercepts to account for correlations of shifts within the same shop and the potentially stronger correlations of shifts within the same shop at the same assessment. Random effects are assumed to be independent. Models for auto and beauty shops will be run separately because of differences in potential covariates for adjusted models.

Covariates for the adjusted models are selected based on their logical relevance and potential impact on exposures. For auto shops, additional covariates will be outside ventilation (i.e., working outside) and average shift apparent temperature. For beauty shops, additional covariates will be baseline air exchange rate and whether the shop offered nail services. The main results will be obtained from the adjusted models, because they provide a more accurate representation by accounting for relevant covariates.

To explore the impact of different model choices, additional adjusted model results will be provided in the Supplemental Material. Specifically, covariates that change the treatment effect by more than 10% when added one-at-a-time as a main effect to the unadjusted model for each sector will be included. The following shift-level covariates at each assessment will be considered: apparent air temperature and self-report activity and ventilation data. The following shop-level covariates at each assessment will also be considered: apparent air temperature; outside TVOC concentration; if the building was rented or owned; if an owner or manager wore a monitor during that shop assessment; self-report activity and ventilation data aggregated to the shop-level; if it was a home business; number of people working that day; number of rooms in shop; if the shop uses "green" products; shop volume (calculated from measured shop dimensions); ventilation data (same categories as those for self-report plus wall heater, personal heater, central heater,

and extractor); and for beauty shops only, air exchange rate and whether the beauty shop provided nail services in addition to hair.

To analyze the secondary outcome of hazard scores derived from specific VOC data, we will use similar mixed models as described above to test the change in hazard score from pre- to post-intervention between the arms (although there will not be a random effect for shift within a shop assessment, because shift-level data are not taken for this outcome). Data preparation, cleaning, and statistical analyses will be performed using R version 4.4.1, the tidyverse package for data wrangling, the lme4 package for linear mixed effects models, and other packages listed in the Supplemental Material.

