United States, with a disproportionate burden faced by Latinos. Small businesses pose a particular risk. They are more likely to employ low-wage Latino workers, and often use hazardous solvents containing volatile organic chemicals that can cause asthma, cancer, cardiovascular, and neurological disease; yet their workers lack access to culturally and linguistically appropriate occupational health and pollution prevention information due to economic, physical, and social barriers. CHW-led interventions and outreach in Latino communities have documented increased access to health care and health education and reduced workplace exposures among farmworkers. CHWs are an innovative method to bridge the gap between these small business communities and other stakeholders. The proposed project will capitalize on established partnerships between the University of Arizona, the Sonora Environmental Research Institute, Inc. and the El Rio Community Health Center. A community-engaged research framework will be used to complete three specific aims: 1) Quantify and identify exposures to hazardous chemicals in the two high risk small business sectors common in our target area (i.e., auto repair shops and beauty salons); 2) Work collaboratively with business owners, trade groups, workers and CHWs to design an industrial hygiene-enhanced CHW intervention tailored for each small business sector; and 3) Conduct a cluster randomized trial to evaluate the effectiveness of the CHW intervention at reducing workplace exposures to volatile organic compounds and assess which factors led to successful utilization of exposure control strategies in both male and female-dominated businesses. Businesses will be randomized to either an intervention or delayed intervention group, both of which will receive incentives to participate, such as worksite health screenings. CHWs will work closely with business owners and employees to select and implement exposure-strategies appropriate for their worksite using a menu of complementary strategies of varying complexity and cost. This innovative project has the potential to directly reduce occupational health disparities through a CHW intervention that moves beyond providing occupational health education. The intervention will overcome current barriers by helping marginalized Latino workers and small business owners who may have limited education, literacy, and computer skills to understand the hazards associated with their work, and will empower them to have greater control over their occupational exposures, with the ultimate goal of preventing occupational disease and reducing health disparities.

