**6) Study Population**

We anticipate that we will obtain personal exposure measurements from *up to 4* workers at 140 businesses (Aim 1 n=20; Aim 3 n=120), as well as conduct focus groups with owners/managers at each business (n=140). Thus, we anticipate that our total subject population could be *700* small business workers and owners. It is possible that at some businesses with <4 workers, we may obtain repeat measurements on different days to ensure that 4 full-shift exposure assessments are conducted at each business during each assessment. This would result in a lower number of participants in our study. We have assumed 3 workers per business (n=420) in calculation of our planned enrollment, in addition to the 140 business owners. We will make every attempt to measure the exposure of the same workers at each assessment. However, because of timing constraints, high worker turnover or staffing changes in the businesses, it is possible that different workers could be measured at each assessment, resulting in a possible total of 1520 (20 business\*4 workers+120 businesses\*4 workers\*3 assessments) worker subjects, in addition to the 140 business owner participants.

Inclusion criteria include workers or owner/managers of small businesses over 18 years of age in the auto repair or beauty salon sectors in southern metropolitan Tucson, Arizona. Exclusion criteria include age less than 18 years or people not working in auto repair or beauty salon sectors.

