## 7) Recruitment Methods and Consenting Process

### a. Recruitment Process:

Businesses will be recruited with the assistance of SERI CHWs and the Tucson Hispanic Chamber of Commerce. The project will be described to the business owner/manager and if they agree to participate and sign the site authorization form, workers will be told about the project's overall goals of community health interventions leading to decreased exposure to potentially dangerous chemicals in their workplace. In Aim 1, we are recruiting 20 businesses so that we can obtain an idea of current baseline VOC exposure levels and work practices, as well as owner/manager and worker ideas about health and safety in the workplace via interviews and focus groups. These are small businesses and SERI CHWs typically go door-to-door and explain the project orally. In Aim 3, we will recruit 120 businesses using the same methods as developed in Aim 1.

In Aim 3, once the business owner/manager agrees for their business to participate and signs the site authorization, the owner/manager will be recruited into the study, allowing the study team to get information about their shop and work practices critical for choosing effective ways of reducing chemical exposures (see *Owner\_Consent* document).

Once the business owner/manager is recruited, individual employees and the owner/manager (if they do similar activities as workers) will be recruited with the goal of measuring four full-shift exposures per business (see *AirSampling\_Consent* document). In Aim 3, we will complete four full-shift exposures in three different visit periods for a total of 12 full-shift exposures per business.

If the small business does not have four workers that are willing to participate, multiple measurements may be taken on the same workers on multiple days. Employees and owner/managers will also be recruited to join focus groups and do interviews, respectively. However, since the shops participating in Aim 1 are not able to participate in the randomized control trial in Aim 3 (for statistical reasons), we will only work with businesses with enough potential participants to consent to complete monitoring for 4 work shifts for any part of Aim 1.

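### Baseline tests in the SAP make no allowance for clustering by shop, so p-values for participant-level characteristics will be too small if workers in the same shop resemble each other (minor)

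*SAP*

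**What the plan says.** The Protocol (Section 3, Background) describes the third aim as follows: "Conduct a cluster randomized trial to evaluate the effectiveness of the CHW intervention". The unit is the shop: "Businesses will be randomized to either an intervention or delayed intervention group". On numbers, "In Aim 3, we will recruit 120 businesses using the same methods as developed in Aim 1" (Recruitment Process), 60 from each sector. Study Population gives the cluster size used for planning: "We have assumed 3 workers per business (n=420) in calculation of our planned enrollment". It allows up to 4 workers per business and expects that some businesses will have fewer.

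The SAP's first paragraph begins "Descriptive statistics will be calculated for shop and participant characteristics". The next sentence sets the comparison of arms: "Differences in baseline characteristics between the immediate and delayed intervention groups will be tested using the Welch Two-Sample t-test for continuous variables". Categorical variables get Fisher's exact test. The sentence after that makes every test two-sided at 0.05. None of these sentences separates shop-level from participant-level variables or mentions clustering. The second paragraph does recognise dependence within a shop, but only for the TVOC outcome, which gets a linear mixed model with random effects for shop and for assessment within shop.

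**The concern.** Welch's and Fisher's tests both treat the observations as independent. When whole shops are randomised and several workers come from each, the difference between arms in a worker characteristic varies more than those tests allow for, provided that workers in one shop are more alike than workers in different shops. The standard error is then too small and so is the p-value.

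The baseline table is where readers judge whether allocation worked. Too many p-values below 0.05 invite the reading that the arms were not comparable at the start. The SAP would also be handling clustering in one table and ignoring it in another.

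**Working it through.** **Inputs**

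- Randomised unit: business (Protocol, Background).
- Shops: 120, or 60 per sector (Protocol, Lay Summary and Recruitment Process).
- Allocation ratio: not stated. Assumed 1:1, so 60 shops per arm overall and 30 per arm within a sector.
- Workers per shop, m: 3 for planning, 4 as the ceiling (Protocol, Study Population). I add 2 because smaller shops are expected.
- ICC of worker characteristics within a shop: not stated. Assumed 0.1 to 0.3, with 0 as reference.

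**The plan's own figures.** 140 × 3 = 420 workers, as stated. The stated maximum also reproduces: 20 × 4 + 120 × 4 × 3 = 80 + 1,440 = 1,520. At 3 per shop, the 120 trial businesses give 360 workers. The documents contain no ICC or design effect to reproduce.

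**True level of an unadjusted test.** The design effect is DE = 1 + (m − 1) × ICC, and the actual two-sided level is 2 × [1 − Φ(1.96/√DE)].

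Example with m = 3 and ICC 0.3: DE = 1 + 2 × 0.3 = 1.6; 1.96/√1.6 = 1.55; level = 12.1%.

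| Workers per shop | ICC 0.1 | ICC 0.2 | ICC 0.3 |
|---|---|---|---|
| 2 | DE 1.1, 6.2% | DE 1.2, 7.4% | DE 1.3, 8.6% |
| 3 | DE 1.2, 7.4% | DE 1.4, 9.8% | DE 1.6, 12.1% |
| 4 | DE 1.3, 8.6% | DE 1.6, 12.1% | DE 1.9, 15.5% |

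With ICC 0, or one worker per shop, DE = 1 and the level is 5.0%.

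**Simulation, Welch** (8,000 runs per setting, 30 shops per arm). At ICC 0.1, 0.2 and 0.3 the level was 7.0%, 9.6% and 12.1% for m = 3, and 8.9%, 12.1% and 16.3% for m = 4. With 60 shops per arm it was 7.4%, 9.4% and 11.8%, and 8.4%, 11.7% and 15.0%. The number of shops makes little difference, as the formula predicts.

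**Simulation, Fisher** (beta-binomial, m = 3, 4,000 runs per setting, prevalence 20% or 50%, 30 or 60 shops per arm). The level was 3.0% to 3.8% at ICC 0, 4.6% to 6.4% at ICC 0.1, 6.7% to 8.9% at ICC 0.2 and 8.5% to 10.5% at ICC 0.3. At 40% prevalence, with 30 shops per arm and m = 3 to 4, it was 6.9% to 9.5% at ICC 0.2 and 9.5% to 12.9% at ICC 0.3. With m = 2 it was about 5.1% at ICC 0.2. The test is conservative under independence, and that offsets a small ICC.

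**Check of the remedy.** Welch's test on one mean per shop gave 4.6% to 5.8% for ICC 0 to 0.5, m = 3 or 4, and 30 or 60 shops per arm. On shop proportions of a binary trait (m = 3) it gave 3.9% to 6.0%.

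**The case against.** Four points can be made for the plan.

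First, the unit of testing is inferred. The words about shops and participants belong to the sentence on descriptive statistics, while the testing sentence speaks only of baseline characteristics. The supplementary models also summarise some self-reported data by shop, so the team could do the same here. This stands as a limit on certainty. Still, the SAP names two independent-observation tests straight after listing participant characteristics and states no aggregation or adjustment. Fisher's test works on counts of categories, which a shop proportion is not.

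Second, the size rests on an ICC that the documents do not give, and shops with 2 workers show less inflation. For categorical variables at a low ICC there is almost none. This stands, and it is why the result is given as a range.

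Third, many characteristics in the SAP are shop-level, with one value per shop. The clustering error does not arise for those. This stands.

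Fourth, a reader might infer that false imbalances lead to the wrong covariates, or distort the treatment effect. The documents do not support that. The main covariates are named in advance on subject-matter grounds, the supplementary ones enter by a 10% change-in-estimate rule, and no baseline p-value enters either route. The TVOC model has its own shop random effects. Adjusting for prespecified covariates is also legitimate in a randomised trial.

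**Conclusion.** Wrong as written, and minor. Followed literally, the SAP gives participant-level baseline p-values that are too small whenever the within-shop ICC is positive and shops contribute more than one worker. With an assumed ICC of 0.1 to 0.3 and 3 to 4 workers per shop, the true level of a nominal 5% Welch test is about 7% to 16%. Fisher's test is near 5% at ICC 0.1 with 3 workers and about 7% to 13% at ICC 0.2 to 0.3 with 3 to 4 workers. These figures rest on the assumed ICC, an assumed 1:1 allocation and the reading that workers are tested individually.

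The error is confined to the participant-level rows of the baseline table. It is no evidence of a failed randomisation, and it leaves the primary result alone. The documents give no list of participant variables, so the number of spurious findings to expect cannot be stated.

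**What to change.** Delete the sentence on baseline significance tests. Report means and SDs, or counts and percentages, by arm and sector, in separate blocks for shops and for participants, with standardised differences if wanted.

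If p-values are kept, state the unit of analysis. Shop-level variables can keep the tests named. Participant-level variables should be compared on shop means or proportions, or in a model with a random intercept for shop.

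The cost is a change of SAP wording. No further data are needed, and dropping the tests reduces the analysis work.

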
## **2) Purpose**

**Project Goal:** Determine if an industrial hygiene-enhanced community health worker (CHW) intervention can significantly reduce workplace exposures to hazardous chemicals in small businesses that mainly employ marginalized minority workers.

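### Does testing unnamed contrasts at 0.05 in two separate sector models inflate the false-positive rate of the primary analysis?

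*SAP*

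**What the plan says.** The SAP's primary-outcome paragraph states the test as "We will use contrasts to test the change in TVOC concentration from pre- to post-intervention between the arms". The unadjusted model has "fixed effects for intervention group (immediate, delayed), assessment time (1, 2, 3), and their two-way interactions", and the adjusted model, named as the source of the main results, adds covariates to it. With two arms and three assessments there are two group-by-time terms. On sectors the SAP says "Models for auto and beauty shops will be run separately because of differences in potential covariates for adjusted models". The threshold is general: "For all analyses, all tests will be two-sided, with a p-value < 0.05 considered statistically significant".

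The Protocol describes the design in two places. Section 3, 1) Background says "Businesses will be randomized to either an intervention or delayed intervention group", and 7a Recruitment Process says of Aim 3 that "we will complete four full-shift exposures in three different visit periods". The goal is put in general terms. Under 2) Purpose the question is whether the intervention "can significantly reduce workplace exposures to hazardous chemicals in small businesses", and Aim 3 is to "evaluate the effectiveness of the CHW intervention at reducing workplace exposures to volatile organic compounds".

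The available text does not say which of assessments 1, 2 and 3 are pre and post, when the delayed arm is treated relative to them, or how two sector results combine into one conclusion. Some Protocol pages are not in the public copy, so the timing may be stated there.

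**The concern.** In a delayed-intervention trial with three assessments, a pre-to-post comparison between arms can mean more than one thing. The 1-to-2 and the 1-to-3 changes are both candidates, and each is available in two sectors. The Purpose reads as a single question, yet two to four tests could bear on it, each at 0.05. If any significant one counted, the chance of a false-positive primary result would exceed 5%. If the tests disagreed, the headline would depend on a choice made after seeing the data.

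The contrasts are also not interchangeable. If the delayed arm were treated between assessments 2 and 3 with an equal, lasting effect, a 1-to-3 contrast would compare treated with treated shops and have an expected value of zero. The secondary hazard score uses the same pre-to-post wording, so it carries the same ambiguity.

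**Working it through.** **Inputs.** Two-sided 0.05 per test; two arms by three assessments; independent random intercepts for shop and for assessment within shop; separate sector models (all from the SAP). There are 60 shops per sector (Protocol 4, Setting). The sectors contain different shops, so their tests are independent. The 0.05 is an input and the documents derive no overall error rate or power, so there is no plan figure to reproduce.

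**One contrast per sector, no true effect.** P(at least one significant) = 1 − 0.95² = 0.0975. Counting only results that favour the intervention: 1 − 0.975² = 0.0494, against 0.025 for a single test.

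**Two contrasts per sector (1-to-2 and 1-to-3).** Let V be the within-shop variance of a shop-assessment mean and n the shops per arm, with balanced data. The shop intercept cancels in a change.
- Variance of each between-arm difference in change: 2V/n + 2V/n = 4V/n.
- Covariance, from the shared assessment 1: V/n + V/n = 2V/n.
- Correlation: (2V/n)/(4V/n) = 0.5, whatever the ICC or number of shops.

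From the bivariate normal at |z| > 1.96, P(at least one) = 0.09075 per sector. Over both sectors: 1 − (1 − 0.09075)² = 0.1733.

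**Which success rule does each figure need?**

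| Reading | False-positive rate |
|---|---|
| Two separate sector questions, one contrast each | 5% in each sector |
| Either sector suffices, one contrast each | 9.75% |
| Both sectors required, one contrast each | 0.05² = 0.25% |
| Any of four contrasts suffices | 17.3% |

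The documents state none of these rules. Sixty shops per sector, different covariates by sector, separate models and no pooled test fit the first row best. So does Aim 2 (Background), which designs the intervention sector by sector.

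**How many contrasts qualify?** A contrast estimates the intervention effect only over an interval in which the delayed arm is untreated. The Lay Summary says Aim 3 compares total VOC readings from before the recommended controls went in with readings from after, for the 120 businesses. The SERI paragraph has the health workers deliver the intervention to every business, and each Aim 3 business has three measurement periods. If delayed shops were treated only after assessment 3, they would have no after reading. Treatment between assessments 2 and 3 fits these statements, and then only the 1-to-2 contrast qualifies. That gives one primary test per sector.

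**What would a correction cost?** Assume 80% power per sector, since the documents give none. With Holm across the two sectors, power at 0.025 is Φ(2.80 − 2.24) = 0.712.
- Both sectors effective: 0.712 + 0.088 × 0.712 = 0.775, about 77%.
- Only one effective: 0.712 + 0.088 × 0.025 = 0.714, about 71%.

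**The case for a change.** The best case for a change is that the text does not exclude the unfavourable readings. The Purpose is one general question, and the SAP's stated reason for splitting the sectors is covariates, not separate hypotheses. The timing inference leans on a lay summary. If the delayed arm were in fact treated after assessment 3, both the 1-to-2 and 1-to-3 contrasts would be valid. Under a constant real effect they would then disagree in 33%, 23% or 13.5% of trials at an assumed 50%, 80% or 90% power each. Naming the contrast would take only a sentence or two.

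Part of this stands. The pre and post assessments are not named, the delayed arm's timing is not given in the available text, and stating both would make the SAP easier to read. The error rates do not stand as a finding against the plan. The SAP never claims a 5% rate across tests, and 9.75% needs an either-sector rule that nobody wrote. The 17.3% also needs two counted contrasts per sector, which the Protocol makes less likely. The disagreement rates rest on that same timing and on assumed power.

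The plural in the SAP sentence is not evidence of several primary tests in one model, because two sectors with unadjusted and adjusted fits already account for it. Choosing the adjusted model in advance also removes one source of selection.

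**Conclusion.** No change is needed. The missing labels for pre and post are a gap that a competent analyst fills from the design, by taking the between-arm difference in change over the interval in which the delayed arm is untreated. On the likelier timing that is assessment 1 to 2, one test per sector at 5%. The same reading carries over to the hazard score. The 10% covariate-change rule, which speaks of a single treatment effect, feeds only supplementary models.

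Declaring the sectors to be separate claims would alter no model, estimate or p-value, because the plan already fits and tests them separately. Correcting across them would guard against a 9.75% either-sector rate (4.9% in the favourable direction) and, at an assumed 80% per-sector power, reduce that power to about 77% or 71%. For two distinct populations with sector-specific interventions, either choice is defensible.

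This rests on the delayed arm being untreated through assessment 2 and treated before assessment 3, and on results being reported by sector. If treatment came after assessment 3 and either contrast were allowed to count, the rate would be 9.1% within a sector. If a single overall claim were drawn from whichever sector was significant, 9.75% would apply even with one contrast per sector.

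### The primary TVOC model has no random intercept for worker although the same workers are to be re-measured: a loss of precision of unknown size, not an invalid test

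*SAP*

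**What the plan says.** The SAP models log TVOC with fixed effects for arm, assessment (1, 2, 3) and their interaction. On the covariance it says that "random effects will be included for shop and assessment time within shop", both as independent random intercepts. The test is described thus: "We will use contrasts to test the change in TVOC concentration from pre- to post-intervention between the arms". The SAP does not say which assessments count as pre and post. Each sector is modelled separately, and the adjusted models supply the main results. The supplemental models vary the covariates and add no worker term.

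The protocol describes who will be measured:
- Section 3, item 6: "We will make every attempt to measure the exposure of the same workers at each assessment".
- The same item allows for turnover: "it is possible that different workers could be measured at each assessment".
- The same item, on enrolment: "We have assumed 3 workers per business (n=420) in calculation of our planned enrollment".
- Item 7a sets four shifts at each of three visit periods, "for a total of 12 full-shift exposures per business".
- Item 7a, for shops without four willing workers: "multiple measurements may be taken on the same workers on multiple days".

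**The concern.** Two shifts by one worker are modelled exactly like shifts by two different workers in the same shop. Worker-to-worker differences therefore sit in the residual. When a worker recurs, that worker's effect partly or wholly cancels from the change between assessments, and the planned model cannot use this. Two things can follow. The standard error can be too large, or the estimate less precise than the data allow. And because the planned model applies one standard error to every pair of assessments, it can understate the error for the pair with the least overlap of workers.

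At stake is power for a primary comparison made separately in each sector, with 60 shops.

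**Working it through.** **Overlap implied by the protocol.** Aim 3 yields 120 × 12 = 1,440 shifts. At three workers per business there are 120 × 3 = 360 workers, so 1,440/360 = 4 shifts each. If all 120 owners also wear a monitor, 1,440/480 = 3 each. In the protocol's full-turnover case there are 120 × 4 × 3 = 1,440 workers, one shift each. Actual overlap is not known.

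**Inputs.** From the documents: 60 shops per sector, three assessments of four shifts, two-sided 5%. The documents contain no power calculation to reproduce. Assumed: 30 shops per arm; variances S (shop) = 0.30, A (assessment within shop), W (worker) and E (residual), with E = 0.30 unless stated. A/W is 0.02/0.40, 0.02/0.20, 0.05/0.30, 0.10/0.30 or 0.20/0.30, giving W:A of 20:1, 10:1, 6:1, 3:1 and 1.5:1. Turnover is zero, complete, or 30% per interval. Variances below are per shop; the arm-size factor cancels from every comparison.

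**Four new workers each time.** Worker and residual cannot be separated, so the two models coincide and nothing is lost.

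**Same four workers throughout.** Worker effects cancel, so the true variance of a change in shop means is 2(A + E/4). The planned model estimates its residual as W + E and its assessment variance as A − W/4. Its variance for the change is 2[(A − W/4) + (W + E)/4] = 2(A + E/4), which is correct as long as W ≤ 4A. Above 4:1 the assessment variance is held at zero and the residual becomes [9(W + E) + 2(4A + E)]/11.
- At 6:1: (9 × 0.60 + 2 × 0.50)/11 = 0.582. Planned variance 0.582/2 = 0.291; true variance 2(0.05 + 0.075) = 0.250. The SE ratio is √(0.291/0.250) = 1.08.
- Where the worker model has 80% power, the planned model has Φ(2.80 − 1.96 × 1.08) = 75%.

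**Three workers, the fourth shift rotating, 30% turnover, at 3:1.** One of the six pairs of shifts in an assessment shares a worker, so the planned residual is E + (5/6)W = 0.30 + 0.25 = 0.55. The true variance of a change is 2A + E/2 + W[0.75 − 2 × (5/16) × r], where r is the retained fraction.
- 1-to-2 and 2-to-3 (r = 0.70): 0.20 + 0.15 + 0.30 × 0.3125 = 0.444.
- 1-to-3 (r = 0.49): 0.35 + 0.30 × 0.44375 = 0.483.
- The planned model uses the average of the three pairs, (0.444 + 0.444 + 0.483)/3 = 0.457, for all of them.
- Type I error, 1-to-2: 2Φ(−1.96 × √(0.457/0.444)) = 4.7%. For 1-to-3: 2Φ(−1.96 × √(0.457/0.483)) = 5.7%.
- Generalised least squares with the worker term gives 0.390. Planned power for 1-to-2 is Φ[(2.80√0.390 − 1.96√0.457)/√0.444] = 74%, against 80%.

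**Large-sample power of the planned model (%), 1-to-2, where the worker model has 80%:**

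| Staffing | 20:1 | 10:1 | 6:1 | 3:1 | 1.5:1 |
|---|---|---|---|---|---|
| Four new each time | 80 | 80 | 80 | 80 | 80 |
| Same four | 60 | 73 | 75 | 80 | 80 |
| Three rotating | 64 | 74 | 76 | 77 | 78 |
| Four, 30% turnover | 64 | 75 | 76 | 77 | 78 |
| Three, 30% turnover | 65 | 74 | 72 | 74 | 76 |

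In these layouts 1-to-2 type I error is 1.1% to 5.0%. With 30% turnover, 1-to-3 type I error is 3.6% to 6.2%. A simulation with 60 shops (20,000 replicates, Wald z) gave 3.7% to 6.1% for 1-to-3, where the z test alone gives about 5.3% under a correct model.

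**Residual variance also matters.** At 3:1 with three workers and 30% turnover, planned power is 74% at E = 0.30, 69% at E = 0.10 and 67% at E = 0.05: losses of 6, 11 and 13 points.

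**Adjusted models.** For beauty the SAP says: "For beauty shops, additional covariates will be baseline air exchange rate and whether the shop offered nail services". Both are shop-level and cannot absorb differences between workers in one shop. In four fitted beauty settings the planned-to-worker SE ratio was 1.08 to 1.12. The auto covariates can act either way. If working outside absorbs half of W, the ratio was 1.01 or 1.03; if shift temperature absorbs half of A, it was 1.08 or 1.11.

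**The case against.** The strongest defence is that shops are randomised and that both shop and shop-by-assessment correlation are modelled, so the primary inference is protected. Under the protocol's stated aim of the same workers at each assessment, four recurring workers cost exactly nothing up to 4:1. The documents fix neither the variances nor the retention rate, so the loss could be zero. All of this stands, and it limits the point to efficiency.

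A reader might go further and infer pseudo-replication and an invalid primary test. The documents do not support that. Inflation of 5.9% to 7.4% for 1-to-3 needs every worker to change between assessments 2 and 3, and 9.4% also needs one worker to cover all four shifts. A 1-to-2 contrast rises to at most 5.7% in the settings run, and only when the 30% turnover falls entirely before assessment 2. In a delayed-intervention design 1-to-3 is also the less natural between-arm contrast, although the documents do not give the timing.

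A reader might also take the worker-to-assessment ratio as enough to cap the loss, or expect the loss always to grow with that ratio. Neither holds: residual variance and overlap matter as much, and the loss is nil at any ratio when all workers differ. Nor are these points a price for adding the term. In an independent set of assumed variances the worst cost of adding it was about 0.2 points, for a 1-to-3 contrast where the planned test was slightly anti-conservative.

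On timing, Protocol Section 2 has the project ending 08/31/22 and the SAP is dated January 16, 2024. Data may already have been collected, so changing the primary model carries a risk of post-hoc choice. That objection stands and shapes the fix.

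**Conclusion.** The omission is real and worth correcting, as an improvement in precision of undetermined size. The planned test remains usable: at or below about 5% type I error for 1-to-2 with equal turnover, and up to about 6% for 1-to-3 with partial turnover.

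The power lost by leaving the term out ranges from nil (all-new workers, or the same four with W at most 4A), through about 2 to 6 points (partial overlap, 1.5:1 to 3:1, E = W), to 11 or more (3:1 with small E). The 15 to 20 point losses in the table need an assumed 20:1 ratio. Every figure rests on assumed variances, turnover and 1:1 allocation; only the design counts come from the documents. That the pre- and post-intervention assessments are not named is a separate gap. It matters here only because the direction of the error depends on it.

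**What to change.** - Add a random intercept for worker nested in shop to the unadjusted and adjusted TVOC models. In lme4, which the SAP already names, this is one extra term.
- Use the participant codes described in Protocol item 12a, after confirming that each worker keeps one code across assessments; the protocol does not say so.
- Make this the primary model only if the choice is fixed before results by arm are examined. Otherwise keep the planned model and report this as a stated sensitivity fit.
- Report the number of distinct workers per shop and how many recur across assessments. This needs no outcome data and shows whether the issue matters here.
- Name the assessments that the pre- to post-intervention contrast compares.

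Cost: one model term, one sentence and one descriptive count. The worker variance may be estimated at or near zero, which returns the planned model, and little is gained if overlap is low. A change of primary model after data collection must be documented as such.
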